Rescue medication should be given if the following occurs:

- There is no improvement in seizure burden within the first 3 hours after administration of BRV.
- Seizure burden is unacceptable to the Investigator, in which case rescue medication can be given earlier at any time, but ideally not in the first 3 hours after the initial administration of BRV.

Subjects in the Confirmatory Cohorts are allowed to switch over from BRV to another AED (eg, MDZ or PHT), if needed. Subjects discontinuing BRV treatment during the Evaluation Period should start the Down-Titration Period while completing the Evaluation Period in parallel for the full 96 hours. In this case, subjects will complete all study assessments, except the collection of blood microsamples for the determination of BRV plasma concentrations. Ideally, changing or adding a new treatment should not occur during the first 3 hours after the initial administration of BRV. Subjects who are switched from BRV to another AED will not be eligible to participate either in the BRV Extension Period or the long-term study.

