3.2.2.2.5 Down Titration Period

Down-Titration Period will start after the Evaluation Period or after the BRV Extension Period, can last up to 1 week. The end of the Down-Titration period is defined as day and time of last BRV administration.

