8.1.6 Responder to other treatment

Responder to other treatment is defined as subject who stopped BRV or switched from BRV to act as a rescue medication and achieved at least 80% reduction (≥ 80 percent change) in non-severe seizure burden from start of other treatment to end of other treatment or at least 50% reduction (≥ 50 percent change) in severe seizure burden measured from initiation of other treatment to end of other treatment during the 96-hour Evaluation Period. Baseline Period for other treatment is defined as 1 hour prior to starting the other treatment. Other treatment Evaluation Period is from the start to the end of other treatment or to the end of 96-hour Evaluation Period if other treatment end is after the 96-hour Evaluation Period.

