- Proportion of subjects who are switched over from BRV to another AED during the 96-hour Evaluation Period [*derivations*: for the numerator calculate the number of subjects who stopped iv BRV and started another AED during the Evaluation Period, the denominator is defined as the number of subjects in the FAS from Confirmatory Cohorts.]
- Proportion of responders to other treatment during the 96-hour Evaluation Period (including at the end of the 96-hour Evaluation Period, and by time intervals: 0 hours to 3 hours, >3 hours to 6 hours, >6 hours to 12 hours, >12 hours to 24 hours, >24 hours to 36 hours, >36 hours to 48 hours, >48 hours to 72 hours, and >72 hours to 96 hours after the start of initial BRV treatment. [*Derivations*: only subjects who switched from BRV to other treatment (stopped BRV due to lack of efficacy) during the 96-hour Evaluation Period will be considered for this variable. See the definition of **responder to other treatment** in [Section 8.1](#). The numerator for proportion of responders to other treatment at the end of 96-hour Evaluation Period is the number of responders to other treatment as defined in [Section 8.1](#); the denominator is the number of subjects in FAS from Confirmatory Cohorts. The numerator for proportion of responders to other treatment during the time intervals: 0-3 hours, >3-6 hours, >6-12 hours, >12-24 hours, >24-36 hours, >36-48 hours, >48-72 hours, >72-96 hours after the start of initial BRV treatment is defined as the number of responders to other treatment with the other treatment stop date and time during 0-3 hours, >3-6 hours,

>6-12 hours, ..., >48-72 hours, >72-96 hours after the start of initial BRV treatment respectively. The denominator is the number of subjects in FAS from Confirmatory Cohorts.]

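### Responders to another treatment are placed in time intervals by when that treatment stopped, so a responder whose replacement AED is still running at 96 hours appears in no interval

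*SAP*

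**What the plan says.** SAP 8.1.6 defines a responder to other treatment by an 80% reduction (nonsevere burden) or a 50% reduction (severe burden) over the course of that treatment, against the hour before it began. The evaluation window runs from start to end of the treatment, "or to the end of 96-hour Evaluation Period if other treatment end is after the 96-hour Evaluation Period".

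SAP 8.3.1 then restricts the variable: "only subjects who switched from BRV to other treatment (stopped BRV due to lack of efficacy) during the 96-hour Evaluation Period will be considered". It gives two kinds of numerator:

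- **Overall:** "The numerator for proportion of responders to other treatment at the end of 96-hour Evaluation Period is the number of responders to other treatment" under the 8.1.6 definition, with no condition on when the treatment stopped.
- **By interval:** "the number of responders to other treatment with the other treatment stop date and time during 0-3 hours", and likewise for each later interval up to >72-96 hours.

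Both use the Confirmatory Cohort FAS as denominator. Protocol 4.2.2 asks for results by the same intervals but does not say how a responder is assigned to one. The neighbouring SAP variable, BRV responders by interval, uses the same eight labels and counts subjects who respond during the interval.

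**The concern.** The two SAP sections do not fit together. One foresees treatment that has not ended by 96 hours. The other admits a responder to a row only through a stop time no later than 96 hours. Nothing in 8.3.1 says what to do with treatment that is still running. The general rules do not help: SAP 4.2.1 leaves a wholly unknown medication end date unimputed.

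Continuation is easy to foresee, because a replacement that controls the seizures may well be kept on. Those successes are the ones that vanish from the time profile, while a responder whose AED was withdrawn is shown, in the interval of withdrawal. A reader comparing these rows with the identically labelled BRV rows would be comparing stop times with response.

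**Working it through.** The documents give no figure for this variable and no formal sample size calculation, so there is nothing to reproduce. The check applies the rules as written.

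**Inputs.** Interval limits 0, 3, 6, 12, 24, 36, 48, 72 and 96 hours (SAP 8.3.1). Denominator N = 36, the planned minimum for the Confirmatory Cohorts (SAP 2.4); the FAS may be smaller. Assumed: R = 6 responders to other treatment, with one replacement AED and so one stop time each.

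**Formula.** Let q be the share of responders whose AED is still running at 96 hours. They have no stop time in any interval, and every other responder has exactly one. Hence:

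sum of interval rows = (R - qR)/N = (1 - q) × R/N, while overall = R/N = 6/36 = 16.7%.

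| q | responders in a row | sum of rows |
|---|---|---|
| 0 | 6 | 6/36 = 16.7% |
| 0.25 | 4.5 | 4.5/36 = 12.5% |
| 0.5 | 3 | 3/36 = 8.3% |
| 0.75 | 1.5 | 1.5/36 = 4.2% |
| 1 | 0 | 0% |

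(Fractional counts only mark points on the line.)

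**Illustration.** Six assumed responders, with AED start and stop in hours after first BRV: 4 to 10; 4 to 80; 5 and ongoing; 10 to 120; 30 and ongoing; 50 to 200.

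- *Stop time as written:* one in >6-12, one in >72-96, four in no row. The rows sum to 2/36 = 5.6% against 16.7% overall. This agrees with the formula at q = 4/6: (1 - 4/6) × 16.7% = 5.6%.
- *Stop time cut at 96 hours:* all six are placed, one in >6-12 and five in >72-96. AEDs begun at 4, 5 and 10 hours all land in the last row.
- *Start time:* all six are placed, three in >3-6 and one each in >6-12, >24-36 and >48-72. The rows sum to 6/36 = 16.7%.

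**The case against.** The strongest defence is that response is defined over the whole course of the other treatment. It is known only when that course ends, so filing by end time follows from the definition. For treatment that continues, 8.1.6 already ends the assessment at 96 hours; a programmer would carry that cut across and put the subject in >72-96. The overall proportion loses nobody, a listing is provided (SAP 8.3.2), and the variable is descriptive and in the lowest tier, with no tests (SAP 4.5).

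Part of this stands. The definition contains no separate time of response, nobody is lost overall, and the stakes are modest. But 8.3.1 refers to the treatment's own stop date and time, and 8.1.6 does not redefine it. Supplying the cut would also give a poor result, since every ongoing treatment goes to the last row whenever it began.

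A reader might also infer that the switch-over count is understated. Its rule reads "for the numerator calculate the number of subjects who stopped iv BRV and started another AED during the Evaluation Period", while the protocol says "Subjects discontinuing BRV treatment during the Evaluation Period should start the Down-Titration Period while completing the Evaluation Period in parallel for the full 96 hours" and SAP 3.2.2.2.5 states "The end of the Down-Titration period is defined as day and time of last BRV administration". That would follow only if BRV counts as stopped at the last tapering dose, and no section says so. Protocol 5.1.2 has BRV stopped and replaced at 96 hours in subjects who do not benefit, and sends those not entering the Extension Period to down-titration; discontinuing likewise comes before it. SAP 3.2.2.2.4 separately recognises the last stable dose. SAP 3.2.2.2.5 dates the end of a study period only, and down-titration is recommended and adjustable, not compulsory.

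Nor are these the only data on replacement of BRV. Disposition (SAP 5.1), concomitant AEDs (6.4.6) and the censoring rule for time to reduction (8.2.4) also bear on it.

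**Conclusion.** The point holds for the interval rows of one variable. Applied as written, SAP 8.3.1 omits from every interval any responder whose replacement AED is still running at 96 hours, and files the rest by stop time. The shortfall against the overall proportion is the fraction q. The (1 - q) relation follows from the rules given one stop time per responder; the 6 of 36 and the values of q are assumptions, and 0% in all eight rows is the extreme case in which every replacement continues.

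The overall proportion at 96 hours, the main secondary endpoint and the historical comparison are unaffected. A claim that the switch rate is understated is not supported.

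**What to change.** In SAP 8.3.1, replace the stop-time condition for the intervals with one of these:

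1. Keep the 8.1.6 definition of response, with its cut at 96 hours, and place each responder in the interval in which other treatment started. Label the rows accordingly. They then sum to the overall proportion.
2. As for BRV responders, count in each interval the subjects on other treatment who meet the 80% or 50% criterion for burden within that interval, against the one-hour pre-treatment baseline. State that a subject may count in several rows, so they need not sum to the overall, and say how an AED begun partway through an interval is handled. List this option in SAP 3.10 as a change to a protocol-defined analysis.

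Carrying the 96-hour cut into the stop time is not a sufficient repair.

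The cost is a wording change and minor reprogramming of one descriptive variable from AED times and VEEG data already collected. Conduct and care do not change. Separately and optionally, a sentence could confirm that, for counting switches, BRV is taken as stopped at the last dose before down-titration.

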8.3.2 Analysis of other efficacy variables

Categorical other efficacy variables will be analyzed using descriptive statistics (counts and proportions with the 95% CIs). Continuous key efficacy variables will be analyzed descriptively as described in [Section 3.1](#).

A listing of other efficacy variables will be provided for the FAS.

9 PHARMACOKINETICS

The PK data, along with the safety data collected from the Exploratory Cohort and the 3 Confirmatory Cohorts, will be reviewed by the DMC. In addition, plasma concentrations of BRV and its metabolites will be monitored and subjected to interpretation on an ongoing basis. The analysis of the PK parameters for the Exploratory and Confirmatory Cohorts will include a sub-analysis for any concomitant use of hypothermia if allowed by the available data.

9.1 Pharmacokinetics

Pharmacokinetics summary tables and listings will be produced on PK-PPS. Listings of the PK parameters and plasma concentrations for all cohorts will be provided.

9.1.1 Exploratory Cohort

Based on the plasma samples collected for the Exploratory Cohort, PK parameters AUC, C_{max} , $t_{1/2}$, volume of distribution, and clearance, will be summarized.

Summary tables will be provided for the PK parameters, for plasma concentrations of BRV, ucb-42145, ucb-100406-1, ucb-107092-1 and of concomitant AEDs (PB and PHT).

The same summary tables for subjects with concomitant hypothermia will be provided.

Individual plots of plasma concentrations over time will be provided.

9.1.2 Confirmatory Cohorts

Based on the plasma samples collected for the Confirmatory Cohorts, PK parameters AUC, C_{max} , $t_{1/2}$, volume of distribution, and clearance, will be summarized.

Summary tables will be provided for the PK parameters, for plasma concentrations of BRV, ucb-42145, ucb-100406-1, ucb-107092-1 and of concomitant AEDs (PB and PHT) for each Confirmatory Cohort separately and overall for combined Confirmatory Cohorts.

Summary tables for subjects with concomitant hypothermia use will be provided for each Confirmatory Cohort separately and overall for combined Confirmatory Cohorts.

Individual plots of plasma concentrations over time will be provided for each Confirmatory Cohort separately and overall for combined Confirmatory Cohorts.

10 SAFETY ANALYSES

All safety analyses will be presented for the SS. Descriptive summaries will be presented overall and by cohorts for

- AEs,

- SAEs,
- physical and neurological examination assessments,
- laboratory results,
- vital signs, (SBP, DBP, respiration rate, heart rate, temperature and oxygen saturation)
- body weight, and
- head circumference.

Following subject characteristics related to safety will also be summarized descriptively:

- cooling status variables (target low body temperature, age since birth when cooling began, duration of cooling [date and start and stop time of cooling], and timing of cooling in relation to first dose of BRV),
- rewarming status variables (duration of rewarming [date and start and stop time of rewarming] and timing of rewarming in relation to first dose of BRV),
- the mother's use of AEDs (including BZD and opiates) at childbirth,
- N-PASS score,
- Thompson score,
- the primary cause of seizure (HIE, hemorrhage, or infarction; CNS malformations; CNS infections; undetermined causes), and
- EEG parameters for the assessment of sedation.

10.1 Extent of exposure

The duration of BRV exposure, is defined as the start date and time of last administration of study medication (BRV) minus the start date and time of first administration of study medication (BRV) plus duration of dosing interval (12 hours, however the dosing interval may be adjusted if results point into that).

The duration of iv BRV exposure during the Evaluation Period will be displayed in hours. The duration of exposure of iv BRV and oral BRV solution during the BRV Extension Period will be displayed in days.

The date and time of last administration of study medication is the maximum date and time from the CRFs “Study Medication Administration (Infusion)” and “Study Medication Administration (Oral Solution)”.

Exposure as categorical parameter will be summarized as number of doses received (1 dose, > 1 dose) and continuous parameter (in hours or days). For the continuous parameter, descriptive statistics for the duration of exposure to study medication in hours or days will be presented. For the number of doses, the number and percentage of subjects who received 1 dose and >1 doses will be summarized. Handling of study medication missing data is described in [Section 4.2.4](#).

Exposure as a continuous parameter will be categorized (>0-12 hours, >12-24 hours, >24-48 hours, >48-72 hours, >72-96 hours, >96 hours – 14 days, >14 days) by study periods for

Exploratory, individual Confirmatory Cohorts and for overall combined Confirmatory Cohorts for the SS.

The following listings will be provided:

- study medication administration,
- exposure to study medication BRV infusion, and
- exposure to study medication BRV oral solution.

10.2 Adverse events

Treatment-emergent adverse events (TEAEs) are defined as AEs which have onset on or after the start date and time of initial study medication (BRV) administration.

10.2.1 General summaries of AEs

A table with overall summary of AEs will be provided separately for Evaluation Period, Extension Period, Down-Titration Period, Safety Follow-up Period and for the entire study, the table will include:

- the numbers and percentages of subjects with at least one TEAE
- the number and percentage of subjects with serious TEAEs
- the number and percentage of subjects with non-serious TEAEs
- the number and percentage of subjects with a TEAE that led to permanent discontinuation of study medication
- the number and percentage of subjects with a drug-related TEAE
- the number and percentage of subjects with a drug-related serious TEAE
- the number and percentage of subjects with a severe TEAE
- the number and percentage of subjects with AE leading to death
- the number and percentage of subjects with TEAEs leading to death
- the number and percentage of subjects who died prior to the first BRV dose

The following summary tables of AEs/TEAEs will be provided by primary SOC and PT. Summaries will be presented by Exploratory Cohort and individual Confirmatory Cohorts and for overall combined Confirmatory Cohorts for the SS.

- Incidence of pre-treatment AEs

Pre-treatment AEs are defined as AEs that had onset strictly prior to the date/time of the first dose of BRV

- Incidence of TEAEs (for Evaluation Period, Extension Period, Down-Titration Period, Safety Follow-up Period and for the entire study)
- Incidence of serious TEAEs
- Incidence of non-serious TEAEs

- Incidence of TEAEs by maximum intensity
Each subject will be counted at most once per primary SOC or PT according to the maximum intensity of all AEs within that SOC or PT. Severe intensity will be assumed for AEs for which intensity is not specified.
- Incidence of drug-related TEAEs
Drug-related AEs are AEs for which the relationship to study medication is specified by the Investigator as Related or AEs for which relationship is not specified.
- Incidence of drug-related serious TEAEs
Drug-related AEs are AEs for which the relationship to study medication is specified by the Investigator as Related or AEs for which relationship is not specified.
- Incidence of TEAEs by relationship
- Incidence of non-serious TEAEs by relationship
- Incidence of serious TEAEs by relationship
- Incidence of fatal TEAEs by relationship
- Incidence of TEAEs leading to permanent discontinuation of study medication
- Incidence of TEAEs leading to death
- Incidence of non-serious TEAEs above reporting threshold of 5% of subjects in any cohort
- Incidence of non-serious TEAEs above reporting threshold of 5% of subjects by relationship
- Incidence of TEAEs of Interest
Defines as a selection of TEAEs identified by UCB to be of interest to BRV. These are identified using an UCB Excel file.

For the incidence of serious TEAE, TEAEs leading to permanent discontinuation of study medication and TEAEs of interest, the summary of subject numbers will be reported.

Listings AE Glossary and all adverse events will be provided for all subjects screened.

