2.4 Determination of sample size

At least 42 evaluable subjects will be enrolled in this study, with at least 6 subjects in the Exploratory Cohort and at least 36 subjects will be enrolled in 3 successive Confirmatory Cohorts, each consisting of 12 subjects. At least 2 subjects undergoing hypothermia treatment will be included in the Exploratory Cohort and each of the 3 Confirmatory Cohorts.

Subjects in the Exploratory Cohort might be replaced due to lack of data, as deemed necessary following the review of PK and safety data by the DMC.

No formal sample size calculation has been performed as a single treatment BRV arm is planned for descriptive summary results and for comparison with the 6 subjects from the Exploratory Cohort. The total number of at least 36 subjects in the Confirmatory Cohorts is expected to provide sufficient evidence of tolerability, safety, and efficacy, as well as good precision for the PK profile of BRV in neonates.

Confirmatory Cohort subjects who drop out or are withdrawn from study participation will not be replaced.

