3.2.2.1.2 Evaluation Period

Evaluation Period starts with the first BRV initiation and will end 48 hours after first BRV initiation.

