3.2.2.2.3 Evaluation Period

Evaluation Period starts when the subject receives first dose of BRV infusion and will last for 96 hours. If subjects do not benefit from BRV treatment after 96 hours of BRV administration, BRV administration will be stopped and replaced by another AED; however, the subject's participation in the study will continue.

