10.4.9 Mechanical ventilation

Mechanical ventilation variables:

– Number and percentage of subjects requiring mechanical ventilation during the Evaluation Period [*derivations*: for subjects from the Exploratory Cohort, the numerator is defined as the number of subjects with the mechanical ventilation start date and time after the initial BRV dose and no later than 48 hours after the start date and time of the initial BRV dose. For subjects from the Confirmatory Cohort, the numerator is defined as the number of subjects with the mechanical ventilation start date and time after the initial BRV dose and no later than 96 hours after the start date and time of the initial BRV dose, the denominator is defined as the number of subjects in the FAS].

– Duration of mechanical ventilation during the Evaluation Period [*derivations*: the duration of mechanical ventilation during the Evaluation Period is defined if the start date and time of the ventilation is after the first BRV dose and not later than 48 hours after the first BRV dose for subjects from the Exploratory Cohort and if the start date and time of the mechanical ventilation is after the first BRV dose and no later than 96 hours after the first BRV dose for subjects from the Confirmatory Cohorts. For subjects from the Exploratory Cohort, the duration is calculated as end date and time of the mechanical ventilation minus the start date and time of the ventilation if the end date and time of the ventilation is no later than 48 hours after the first BRV dose for subjects. If the end date and time of the ventilation is later than 48 hours after the first BRV dose, then the duration is calculated as 48 hours minus start date and time of the ventilation. For

subjects from the Confirmatory Cohorts, the duration is calculated as end date and time of the ventilation minus the start date and time of the ventilation if the end date and time of the mechanical ventilation is no later than 96 hours after the first BRV dose. If the end date and time of the ventilation is later than 96 hours after the first BRV dose, then the duration is calculated as 96 hours minus start date and time of the ventilation. The duration is calculated in hours, i.e. the number of days is multiplied by 24, then the number of hours added, and the number of minutes divided by 60 is added].

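### Evaluation-Period adverse event and ventilation tables set a 48-hour Exploratory window beside a 96-hour Confirmatory window under one label, so a cross-cohort reading can show a difference with no dose effect

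*SAP*

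**What the plan says.** **Windows.** SAP 3.2.2.1.2 defines the Exploratory window: "Evaluation Period starts with the first BRV initiation and will end 48 hours after first BRV initiation". SAP 3.2.2.2.3 defines the Confirmatory window: "Evaluation Period starts when the subject receives first dose of BRV infusion and will last for 96 hours".

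**Adverse events.** SAP 10.2.1 gives the overview by period ("A table with overall summary of AEs will be provided separately for Evaluation Period, Extension Period") and does the same for one table by system organ class and preferred term: "Incidence of TEAEs (for Evaluation Period, Extension Period, Down-Titration Period, Safety Follow-up Period and for the entire study". For the class and term tables it adds: "Summaries will be presented by Exploratory Cohort and individual Confirmatory Cohorts and for overall combined Confirmatory Cohorts for the SS". The opening of SAP 10 says adverse event summaries are given overall and by cohort, which covers the overview too. The remaining tables in 10.2.1 (for example serious, drug-related, by intensity, leading to discontinuation) name no period.

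**Ventilation.** SAP 10.4.9 counts an Exploratory subject if ventilation starts after the first dose and "no later than 48 hours after the start date and time of the initial BRV dose". For a Confirmatory subject the limit is "no later than 96 hours after the start date and time of the initial BRV dose". Duration is cut off at 48 h or 96 h in the same way, and the table is presented by individual cohort.

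**Comparison.** SAP 2.4 (and Protocol 13.9, in nearly the same words) says the single arm is planned "for descriptive summary results and for comparison with the 6 subjects from the Exploratory Cohort".

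**Doses.** Protocol 7.2 gives 0.5 mg/kg bid for the Exploratory Cohort and 1 mg/kg bid for the Confirmatory Cohorts.

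**The concern.** Observation time doubles exactly where the dose doubles, so in these tables window length and dose cannot be separated. The columns carry the same label, and neither SAP 10.2.1 nor 10.4.9 plans a common cut-off or an exposure-adjusted rate.

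Short-term safety is a secondary objective, and adverse events are the secondary safety variable. Efficacy is analysed in the Confirmatory Cohorts only, so any comparison with the 6 Exploratory subjects can concern only PK or safety. A reader looking for a dose-related safety signal in neonates would turn to these tables, and they lean one way even if brivaracetam affects neither outcome. What is at stake is a misread table, not a false test result.

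**Working it through.** The documents give no background rate for adverse events or ventilation and no figure for a window effect, so there is nothing of the plan's own to reproduce. The rates below are assumptions, shown as a range. Dose is taken to have no effect throughout.

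**1. Incidence, constant hazard.** Let p48 be the 48-h incidence. Then p96 = 1 − (1 − p48)², and the ratio is p96 / p48 = 2 − p48.

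| Assumed 48-h incidence | 96-h incidence | Ratio |
|---|---|---|
| 5% | 9.8% | 1.95 |
| 10% | 19% | 1.90 |
| 30% | 51% | 1.70 |
| 50% | 75% | 1.50 |
| 80% | 96% | 1.20 |
| 90% | 99% | 1.10 |

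The ratio approaches 2 only for rare events and falls toward 1 for common ones.

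**2. Incidence, other hazard shapes.** With cumulative hazard proportional to t^k, p96 = 1 − (1 − p48)^(2^k).

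- Front-loaded events, k = 0.5: ratio 1.40 at a 48-h incidence of 5%, falling to 1.12 at 80%.
- Rising hazard, k = 1.5: ratio 2.70 at 5%, falling to 1.24 at 80%.

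**3. Ventilation duration, long spells.** For ventilation that starts s hours after the first dose (s below 48) and continues past 96 h, the recorded durations are 48 − s and 96 − s.

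- s = 0: 96/48 = 2.0
- s = 12: 84/36 = 2.33
- s = 24: 72/24 = 3.0
- s = 36: 60/12 = 5.0

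**4. Ventilation duration, mixed spells.** This was simulated with 2,000,000 draws, a constant start hazard (48-h incidence 5% to 20%) and exponential spell lengths. The ratio of mean recorded duration among ventilated subjects was:

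- mean spell 6 h: 1.07
- mean spell 24 h: 1.34 to 1.35
- mean spell 72 h: 1.67 to 1.70
- spells that never end: 2.02 to 2.07

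**5. After the fix.** If every cohort counts only onsets in the first 48 h and caps ventilation at 48 h, the ratio is 1.00 for incidence and for duration, whatever the hazard shape. Events per subject-hour at risk would also give 1.00, but only under a constant hazard, so the common window is the safer choice.

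**The case against.** **Entire-study tables exist.** The adverse event overview and the treatment-emergent incidence table are also produced for the entire study, where Exploratory onsets after 48 h are counted. This stands and softens the point. It does not settle it, because total follow-up also differs by cohort: only Confirmatory subjects have a Down-Titration Period, and under the current protocol only they may stay in the Extension Period to 90 days of postnatal age. Ventilation has no entire-study summary.

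**Most adverse event tables are outside the point.** A reader might infer that all of SAP 10.2.1 is affected. The text supports this for two outputs only, since the others name no period.

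**The comparison is thinly stated.** A reader might infer a planned dose-safety contrast. The documents do not go that far. The support is one sample-size sentence that names neither safety nor dose, and before Protocol Amendment 5 that sentence referred to midazolam-treated Exploratory subjects (Protocol 17.5). SAP 4.5 calls all analyses descriptive, with no tests. The dose recommendation of 05 Nov 2020 has already been made, and Protocol 5.1 bases later adjustment on Confirmatory data, which share one window. All this limits the consequence. The current text still announces a comparison and still places the columns side by side.

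**The comparison is weak anyway.** One event in 6 has an exact 95% confidence interval of 0.4% to 64%. Exploratory doses 2 to 4 are at the Investigator's discretion, and the concomitant antiepileptic rules differ between the steps. This also stands, but imprecision does not remove a bias in one direction, and this confounder is cheap to take out.

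**The reader can see the windows.** They are defined in the SAP, and exposure is summarised by period and cohort (SAP 10.1), with listings by subject. That reveals the imbalance without adjusting for it.

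**Conclusion.** The point holds in a limited form. In the Evaluation-Period adverse event overview, the treatment-emergent incidence table and the ventilation table, a 48-h window stands beside a 96-h window. A descriptive cross-cohort reading can then show a higher rate or longer ventilation with no dose effect.

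The size depends on assumptions the documents cannot supply. A reader might infer that Confirmatory figures are inflated up to twofold. That is not a general bound. For incidence, 2 is the rare-event limit under a constant hazard; the inflation is smaller for common or front-loaded events and can be larger if hazard rises. For ventilation duration, 2 is not a ceiling: the ratio is close to 1 for short spells and can pass 2 when a spell starts late and outlasts 96 h.

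No formal conclusion of the trial is at risk. The change is worth making because the artefact is systematic, coincides with the dose step, and is easy to remove.

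**What to change.** In SAP 10.2.1, add a 0 to 48 h tabulation, counted from the first brivaracetam dose, for the Confirmatory Cohorts in the Evaluation-Period adverse event overview and in the treatment-emergent incidence table. In SAP 10.4.9, add the same for the ventilation count, and for duration with a cap at 48 h. State that any Exploratory versus Confirmatory reading uses this column. Keep the 0 to 96 h results for the Confirmatory Cohorts and label each column with its window.

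SAP 10.4.4 already works this way for the Sarnat scale: 24 h and 48 h for all cohorts, 72 h and 96 h for the Confirmatory Cohorts only.

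The cost is SAP wording, programming and one extra column per table. No new data are needed, because the SAP already uses date and time for adverse event onset (10.2) and for ventilation start and end (10.4.9). The change does not make the comparison precise: there are still 6 Exploratory subjects, and the cohorts differ in other ways, so it stays descriptive.
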